## 5.8 Volume of blood

The total volume of blood that will be drawn from each patient for this study is listed in Table 3 below. The collection of additional samples is performed locally at the discretion of the investigator and recorded in the eCRF as appropriate, thus requiring additional sample volumes.

**Table 3** Volume of blood to be withdrawn from each patient

Assessment	Sample Volume (mL)	No. of samples Visit 1	Total volume Visit 1 (mL)	No. of samples Visit 2	Total volume Visit 2 (mL)	No. of samples Visit 3	Total volume Visit 3 (mL)	No. of samples Visit 4	Total volume Visit 4 (mL)	No. of samples Visit 5	Total volume Visit 5 (mL)	Total (mL)
Haematology	5	1	5	0	0	0	0	1	5	1	5	15
Clinical Chemistry	5	1	5	0	0	0	0	1	5	1	5	15
Coagulation	3	1	3	0	0	0	0	0	0	0	0	03
Virology Screen	4	1	4	0	0	0	0	0	0	0	0	04
PRU	4	0	0	2	8	2	8	0	0	0	0	16
Pharmacokinetic	2	0	0	1	2	2	4	0	0	0	0	06
Biomarkers	8.5	0	0	1	8.5	1	8.5	1	8.5	0	0	25.5
Total			17		18.5		20.5		18.5		10	84.5

## **6. SAFETY REPORTING AND MEDICAL MANAGEMENT**

The PI is responsible for ensuring that all staff members involved in the study are familiar with the content of this section.

### **6.1 Definition of adverse events**

An AE is the development of an undesirable medical condition or the deterioration of a pre-existing medical condition following or during exposure to a pharmaceutical product, whether or not considered causally related to the product. An undesirable medical condition can be symptoms (e.g., nausea, chest pain), signs (e.g., tachycardia, enlarged liver) or the abnormal results of an investigation (e.g., laboratory findings, electrocardiogram). In clinical studies, an AE can include an undesirable medical condition occurring at any time, including run-in or washout periods, even if no study treatment has been administered.

The term AE is used to include both serious and non-serious AEs.

### **6.2 Definitions of serious adverse event**

A serious adverse event (SAE) is an AE occurring during any study phase (i.e., run-in, treatment, follow-up), that fulfils 1 or more of the following criteria:

- Results in death
- Is immediately life-threatening
- Requires in-patient hospitalisation or prolongation of existing hospitalisation
- Results in persistent or significant disability/incapacity or substantial disruption of the ability to conduct normal life functions
- Is a congenital abnormality or birth defect
- Is an important medical event that may jeopardise the patient or may require medical intervention to prevent 1 of the outcomes listed above.

For further guidance on the definition of a SAE, see [Appendix B](#) to the Clinical Study Protocol.

### **6.3 Recording of adverse events**

#### **6.3.1 Time period for collection of AEs**

AEs and SAEs will be collected from the time of informed consent and throughout the study including follow-up period (up to Visit 6).

### **6.3.2 Follow-up of unresolved adverse events**

Any AEs that are unresolved at the patient's last AE assessment in the study are followed up by the Investigator for as long as medically indicated, but without further recording in the eCRF. AZ retains the right to request additional information for any patient with ongoing AE(s)/SAE(s) at the end of the study, if judged necessary.

### **6.3.3 Variables**

The following variables will be collect for each AE;

- AE (verbatim)
- The date and time when the AE started and stopped
- Maximum intensity
- Whether the AE is serious or not
- Investigator causality rating against the IP (yes or no)
- Action taken with regard to IP
- AE caused patient's withdrawal from study (yes or no)
- Outcome

In addition, the following variables will be collected for SAEs:

- Date AE met criteria for SAE
- Date Investigator became aware of SAE
- AE is serious due to
- Date of hospitalisation
- Date of discharge
- Probable cause of death
- Date of death
- Autopsy performed
- Causality assessment in relation to Study procedure(s)
- Causality assessment in relation to other medication
- Description of AE

It is important to distinguish between serious and severe AEs. Severity is a measure of intensity whereas seriousness is defined by the criteria in Section 6.2. An AE of severe intensity need not necessarily be considered serious. For example, nausea that persists for several hours may be considered severe nausea, but not a SAE unless it meets the criteria shown in Section 6.2. On the other hand, a stroke that results in only a limited degree of disability may be considered a mild stroke but would be a SAE when it satisfies the criteria shown in Section 6.2.

The definitions for intensity rating are:

- Mild (awareness of sign or symptom, but easily tolerated)
- Moderate (discomfort sufficient to cause interference with normal activities)
- Severe (incapacitating, with inability to perform normal activities)

#### **6.3.4 Causality collection**

The Investigator will assess causal relationship between IP and each AE, and answer ‘yes’ or ‘no’ to the question ‘Do you consider that there is a reasonable possibility that the event may have been caused by the investigational product?’

For SAEs causal relationship will also be assessed for other medication and study procedures. Note that for SAEs that could be associated with any study procedure the causal relationship is implied as ‘yes’.

A guide to the interpretation of the causality question is found in [Appendix B](#) to the Clinical Study Protocol.

#### **6.3.5 Adverse events based on signs and symptoms**

All AEs spontaneously reported by the patient or care provider or reported in response to the open question from the study personnel: ‘Have you had any health problems since the previous visit/you were last asked?’, or revealed by observation will be collected and recorded in the eCRF. When collecting AEs, the recording of diagnoses is preferred (when possible) to recording a list of signs and symptoms. However, if a diagnosis is known and there are other signs or symptoms that are not generally part of the diagnosis, the diagnosis and each sign or symptom will be recorded separately.

#### **6.3.6 Adverse events based on examinations and tests**

The results from protocol mandated laboratory tests and vital signs will be summarised in the CSR. Deterioration as compared to baseline in protocol-mandated laboratory values, vital signs should therefore only be reported as AEs if they fulfil any of the SAE criteria or are the reason for discontinuation of treatment with the IP.

If deterioration in a laboratory value/vital sign is associated with clinical signs and symptoms, the sign or symptom will be reported as an AE and the associated laboratory result/vital sign will be considered as additional information. Wherever possible the reporting Investigator uses the clinical, rather than the laboratory term (e.g., anaemia versus low haemoglobin [Hb] value). In the absence of clinical signs or symptoms, clinically relevant deteriorations in non-mandated parameters should be reported as AE(s).

Any new or aggravated clinically relevant abnormal medical finding at a physical examination as compared with the baseline assessment will be reported as an AE.

### 6.3.7 Hy's Law

Cases where a patient shows elevations in liver biochemistry may require further evaluation and occurrences of AST or ALT  $\geq 3xULN$  together with total bilirubin  $\geq 2xULN$  may need to be reported as SAEs. Please refer to [Appendix D](#) for further instruction on cases of increases in liver biochemistry and evaluation of Hy's Law.

### 6.3.8 Assessment of bleeding events

One of the safety objectives in this study is to determine the percent of patients with haemorrhagic events requiring medical intervention. Bleeding events will be recorded as AEs. The investigator will do the classification of bleeding events; there will be no committee for adjudication of these events.

Bleeding events will be recorded in the bleeding event eCRF.

For patients experiencing a bleeding event that fulfils criteria in more than 1 category, the bleed will be assigned to the most severe category. The bleeding definitions ([Mitchell et al 2011](#)) are:

**Major bleeding:** defined as any fatal bleeding, clinically overt bleeding associated with a decrease in Hb of at least 20 g L (2 g dL), bleeding that is retroperitoneal, pulmonary, intracranial, or otherwise involves the central nervous system or bleeding that requires surgical intervention in an operating suite.

**Clinically relevant non-major bleeding:** defined as overt bleeding for which a blood product is administered and which is not directly attributable to the patient's underlying medical condition, and bleeding that requires medical or surgical intervention to restore hemostasis, other than in an operating suite.

**Minor bleeding:** defined as any overt or macroscopic evidence of bleeding that does not fulfil the above criteria for either major bleeding or clinically relevant, non-major bleeding. Menstrual bleeding resulting in a medical consultation and/or intervention will be classified as a minor bleeding event.

### 6.3.9 Vaso-occlusive crisis (VOCs)

If a VOC event fulfils any criteria of an SAE according to the definition (see [Appendix B](#)) or result in discontinuation of IP, it should be reported both on the eCRF VOC module and as an SAE or AE respectively. For reporting and definition of VOC see Section [5.1.2](#).

## 6.4 Reporting of serious adverse events

All SAEs have to be reported, whether or not considered causally related to the IP, or to the study procedure(s). All SAEs will be recorded in the eCRF.

If any SAE occurs in the course of the study, then Investigators or other site personnel inform the appropriate AZ representatives within 1 day i.e., immediately but **no later than 24 hours** of when he or she becomes aware of it.

The designated AZ representative works with the Investigator to ensure that all the necessary information is provided to the AZ Patient Safety data entry site **within 1 calendar day** of initial receipt for fatal and life threatening events **and within 5 calendar days** of initial receipt for all other SAEs.

For fatal or life-threatening AEs where important or relevant information is missing, active follow-up is undertaken immediately. Investigators or other site personnel inform AZ representatives of any follow-up information on a previously reported SAE within 1 calendar day i.e., immediately but **no later than 24 hours** of when he or she becomes aware of it.

Once the Investigators or other site personnel indicate an AE is serious in the WBDC system, an automated email alert is sent to the designated AZ representative.

If the WBDC system is not available, then the Investigator or other study site personnel reports a SAE to the appropriate AZ representative by telephone.

The AZ representative will advise the Investigator/study site personnel how to proceed.

The reference document for definition of expectedness/listedness is the IB for the AZ drug.

## **6.5 Overdose**

An overdose is considered any dose greater than that specified in the protocol.

There is currently no known antidote to reverse the effects of ticagrelor, and ticagrelor is not expected to be dialysable. Treatment of overdose should follow local standard medical practice. The expected effect of excessive ticagrelor dosing is prolonged duration of bleeding risk associated with platelet inhibition. If bleeding occurs appropriate supportive measures should be taken.

In healthy adults, ticagrelor is well tolerated in single doses up to 900 mg. Gastrointestinal toxicity (nausea, vomiting, diarrhoea) was dose-limiting in healthy adults following ascending single doses. Other clinically meaningful adverse effects, which may occur with overdose, include dyspnoea and ventricular pauses. In the event of overdose, observe for these potential adverse effects, and consider ECG monitoring. Measure platelet inhibition with VerifyNow to determine the extent and duration of excessive platelet inhibition.

- An overdose with associated AEs is recorded as the AE diagnosis/symptoms on the relevant AE modules in the eCRF and on the Overdose eCRF module.
- An overdose without associated symptoms is only reported on the Overdose eCRF module.

If an overdose on an AZ study drug occurs in the course of the study, then the Investigator or other site personnel inform appropriate AZ representatives immediately, or **no later than 24 hours** of when he or she becomes aware of it.

The designated AZ representative works with the Investigator to ensure that all relevant information is provided to the AZ Patient Safety data entry site.

For overdoses associated with a SAE, the standard reporting timelines apply, see Section 6.4. For other overdoses, reporting must occur within 30 days.

## **6.6 Pregnancy**

All pregnancies and outcomes of pregnancy should be reported to AZ representatives.

### **6.6.1 Maternal exposure**

If a patient becomes pregnant during the course of the study IP should be discontinued immediately.

Pregnancy itself is not regarded as an AE unless there is a suspicion that the IP under study may have interfered with the effectiveness of a contraceptive medication. Congenital abnormalities/birth defects and spontaneous miscarriages should be reported and handled as SAEs. Elective abortions without complications should not be handled as AEs. The outcome of all pregnancies (spontaneous miscarriage, elective termination, ectopic pregnancy, normal birth or congenital abnormality) should be followed up and documented even if the patient was discontinued from the study.

If any pregnancy occurs in the course of the study, then the Investigator or other site personnel informs the appropriate AZ representatives within 1 day i.e., immediately but **no later than 24 hours** of when he or she becomes aware of it.

The designated AZ representative works with the Investigator to ensure that all relevant information is provided to the AZ Patient Safety data entry site within 1 or 5 calendar days for SAEs (see Section 6.4) and within 30 days for all other pregnancies.

The same timelines apply when outcome information is available.

The PREGREP module in the eCRF is used to report the pregnancy and the PREGOUT is used to report the outcome of the pregnancy.

## **6.7 Management of IP related toxicities**

Please see Section 3.9.2.

## **6.8 Study governance and oversight**

There will be no Independent Data Monitoring Committee in this study. The safety of all AstraZeneca clinical studies is closely monitored on an on-going basis by AstraZeneca

representatives in consultation with Patient Safety. Issues identified will be addressed; for instance this could involve amendments to the study protocol and letters to Investigators.

## 7. INVESTIGATIONAL PRODUCT AND OTHER TREATMENTS

### 7.1 Identity of investigational product(s)

Investigational product	Dosage form and strength	Manufacturer
Ticagrelor 10 mg tablet	Plain, round, biconvex, white/off-white, tablet, 10 mg	AstraZeneca
Ticagrelor 45 mg film-coated tablet	Plain, round, biconvex, yellow, film-coated tablet, 45 mg	AstraZeneca
Placebo for ticagrelor 10 mg tablet	Plain, round, biconvex, white/off-white, tablet containing no active ingredient	AstraZeneca
Placebo for ticagrelor 45 mg film-coated tablet	Plain, round, biconvex, yellow, film-coated tablet containing no active ingredient	AstraZeneca

Ticagrelor tablets of 10 mg, 45 mg and their matching placebos will be packed in high-density polyethylene bottles.

### 7.2 Dose and treatment regimens

#### Treatment during single-blind run-in period

During the 4 week single-blind run-in treatment period eligible patients will receive:

- Matching placebo for ticagrelor 10 mg + matching placebo for ticagrelor 45 mg, 1 tablet bid given orally from each bottle

Study drug bottles will be managed via the IVRS/IWRS and at Visit 1 first dose of the study drug from each bottle will be administered at the clinic by site staff. Subsequent doses should be taken morning and evening, at approximately 12 hour intervals.

#### Treatment during double-blind randomisation period

Randomisation to bid double-blind treatment with ticagrelor or placebo will occur at Visit 2 via the IVRS/IWRS. Eligible patients will be randomly assigned to 1 of 3 treatment regimens:

- Ticagrelor 10 mg + matching placebo for ticagrelor 45 mg, 1 tablet bid given orally from each bottle
- Ticagrelor 45 mg + matching placebo for ticagrelor 10 mg, 1 tablet bid given orally from each bottle

- Matching placebo for ticagrelor 10 mg + matching placebo for ticagrelor 45 mg, 1 tablet bid given orally from each bottle

At Visit 2, the first dose of the study drug from each bottle will be administered at the clinic by site staff as soon as possible after randomisation. Subsequent doses should be taken morning and evening, at approximately 12 hour intervals.

At Visit 3 patient should not take their morning dose at home and it should be administered after obtaining the '0' hour (Pre-dose) PRU and PK samples.

Study drug should be swallowed whole with water. Study drug should not be altered (e.g., crushed, put in another vehicle) and should not be given by other routes.

### **7.3 Labelling**

Labels will be prepared in accordance with Good Manufacturing Practice (GMP) and local regulatory guidelines. The labels will fulfil GMP Annex 13 requirements for labelling. Label text will be translated into local language.

### **7.4 Storage**

All study drugs should be kept in a secure place under appropriate storage conditions and in original container. The study drug label on the bottle specifies the appropriate storage.

### **7.5 Compliance**

The administration of all study drugs (including IPs) should be recorded in the appropriate sections of the eCRF.

Each time study drug is dispensed, compliance will be reinforced. When study drug is returned, compliance will be assessed based upon an interview with the subject and a count of the tablets returned which should be  $\geq 80\%$  of that prescribed. Noncompliance with study drug will be considered as protocol deviations. Missed doses of ticagrelor or placebo blinded study drug should not be compensated (i.e., if a dose is missed the next regularly scheduled dose should be taken and should not be doubled).

### **7.6 Accountability**

The study drug provided for this study will be used only as directed in the study protocol. The study personnel will account for all study drugs dispensed to and returned from the patient.

Patient will be asked to bring all unused study drug and empty bottles to the study site at each on-site visit. The Investigator or delegate will enter the amount of returned tablets in the eCRF (except Visit 3) and make an assessment regarding patient treatment compliance. Any patient found to be noncompliant would be counselled on the importance of taking their study drug as prescribed.

Study site personnel or the AZ delegated monitor will account for all study drugs received at the site, unused study drugs and for appropriate destruction. Certificates of delivery, destruction and return should be signed.

## **7.7 Concomitant and other treatments**

Use of ADP receptor blockers (e.g., clopidogrel, prasugrel, ticlopidine), dipyridamole and cilostazol is not allowed in the study.

Treatment with oral or parenteral anticoagulants, and daily aspirin or non-steroidal anti-inflammatory agents (requiring treatment >3 days/week) is not allowed in the study except for prophylactic doses of heparins, e.g., flushing of catheters (see exclusion criteria in Section 3.2).

### **CYP3A4 inhibitors**

Concomitant use of strong inhibitors of CYP3A4 (e.g., atazanavir, boceprevir, clarithromycin, [but not erythromycin or azithromycin], conivaptan, indinavir, itraconazole, ketoconazole, lopinavir/ritonavir, mibefradil, nefazodone, nelfinavir, posaconazole, ritonavir, saquinavir, telaprevir, telithromycin, voriconazole) is not allowed.

### **CYP3A4 substrates or inducers**

Co-administration of CYP3A4 substrates with a narrow therapeutic index is not allowed. Co-administration of strong inducers of CYP3A4 (e.g., rifampin/rifampicin, rifabutin, phenytoin, carbamazepine, phenobarbital, avasimibe, St. John's wort) is not allowed.

### **P-glycoprotein interactions**

Ticagrelor is a weak inhibitor of P-glycoprotein (P-gp), a drug efflux transporter. Digoxin is a substrate of P-gp and concurrent treatment with ticagrelor modestly increases digoxin levels. If the patient is receiving digoxin, levels should be monitored closely following initiation of IP and with any change in IP.

#### **7.7.1 Blood transfusions**

If a patient requires any blood transfusion during the study, this information will be captured in the eCRF.

#### **7.7.2 Other concomitant treatment**

If a patient is taking HU, they must have been on the drug for 6 months or more and the dose stabilised for at least 3 months, and the dosing should not be altered or terminated throughout the 16-week study treatment period, other than for safety reasons.

If a patient is taking erythropoietin at Screening, they must have been on the drug for 6 months or more and the dose stabilised for at least 3 months.

Other medication other than that described above, which is considered necessary for the patient's safety and well-being, may be given at the discretion of the Investigator and recorded in the appropriate sections of the eCRF. The entry must include the dose, regimen, route, indication, and dates of use.

Patients may not participate in any other interventional drug study for at least 30 days prior to starting this study and may not participate in any other interventional drug study throughout the study period.

## **7.8 Post Study Access to Study Treatment (Not Applicable)**

## **8. STATISTICAL ANALYSES BY ASTRAZENECA OR DELEGATE**

### **8.1 Statistical considerations**

A comprehensive Statistical Analysis Plan (SAP) will be prepared prior to first patient in and any subsequent amendments will be documented, with final amendments completed prior to unblinding of the data. The analysis of this study will be performed by AZ or AZ delegate.

### **8.2 Sample size estimate**

A sample size of 30 patients per group provides the ability to detect a difference in proportion of days with pain of 0.17 (17 percentage points) by use of a 90% confidence interval. Basis for this assumption is a placebo level of 0.56 with a SD of approximately 0.4 (PISCES and a prasugrel study in both cases – [Wun et al 2013](#), [Smith et al 2008](#)).

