## **8.4 Outcome measures for analyses (Not Applicable)**

### **8.5 Methods for statistical analyses**

No statistical comparisons are planned for the primary objective. PRO and safety measures will be summarized descriptively using respective analysis set.

In general, all efficacy, safety, plasma concentrations of ticagrelor and active metabolite, PRU and PRO variables will be presented using descriptive statistics and graphs as appropriate. Continuous variables will be presented with descriptive statistics (n, mean, standard deviation [SD], median, min, max), within treatment group. Geometric mean and coefficient of variation (CV) will be used instead of arithmetic mean and SD, if appropriate, with CV(%) calculated as:

$$100 \cdot \sqrt{(\exp(s^2) - 1)}$$

where s is the SD of the data on a log scale.

Categorical variables will be summarized in frequency tables (number of patients and percentage), by treatment group. Data will also be presented in individual patient listings.

The presentation of pain, intensity of pain and days of analgesic use due to SCD, will be presented by week. They will also be presented by subgroup of PGIC, divided into 3 groups, improved (1 and 2), no change (3, 4 and 5) and worse (6 and 7).

In general, baseline values will be the closest observation prior to the first administration of randomised IP. For the baseline value of pain, intensity of pain and days of analgesic use, a mean value for the 4 weeks in the Screening period will be calculated.

The number of days with pain due to SCD and the analysis of analgesic use due to SCD will be analysed using an ANCOVA model, with treatment, country, baseline average value, and baseline hydroxyurea (HU) use as explanatory variables, and treatment and HU as fixed effects and centre as a random effect. Least squares differences in means between ticagrelor 45 mg and placebo and ticagrelor 10 mg and placebo with corresponding 90% confidence interval will be presented. The objectives will be analysed as a proportion of days, during the whole treatment period. A sensitivity analysis of pain and analgesic use will be performed using the ANCOVA model but excluding country and baseline HU use.

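### Section 8.2 calls 0.17 a detectable difference, but on its own inputs 0.17 is the half-width of the unadjusted 90% CI, which a true difference of 0.17 clears only about half the time

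*Protocol*

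**What the plan says.** Section 8.2 (Sample size estimate) is the protocol's only justification for the group size. It states that a sample of 30 patients per group "provides the ability to detect a difference in proportion of days with pain of 0.17 (17 percentage points"), and names the criterion: "by use of a 90% confidence interval". The inputs are "a placebo level of 0.56 with a SD of approximately 0.4", attributed to two cited studies. The section states no power or other probability of detection and makes no allowance for withdrawals.

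Section 8.5 (Methods for statistical analyses) plans an ANCOVA of the proportion of days over the whole treatment period, with the baseline average among the explanatory variables. It presents the least squares difference of each dose from placebo with a 90% CI. The same section says: "No statistical comparisons are planned for the primary objective".

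Section 3.10.2 says that patients who withdraw after randomisation are not replaced.

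**The concern.** To say that a sample size can detect a given difference is normally to say that, if the difference is real, the trial will probably show it. Section 8.2 attaches no probability to the claim, so the reader cannot tell what 0.17 stands for. The inputs show that it is the margin of error of the comparison, that is, a threshold for the observed difference. A true effect equal to that threshold is found only about as often as it is missed.

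What is at stake is how the design and its result are read. Section 2.1 makes the efficacy of the two doses in reducing pain days the primary objective. Someone relying on Section 8.2 could take an interval that includes zero as evidence against a 17-point effect, although on the section's own inputs the design would often miss such an effect. That misreading is an inference about readers; the protocol does not state it.

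**Working it through.** **Inputs.** From Section 8.2: n = 30 per group, SD = 0.4, and a 90% CI, read as two-sided (z = 1.645). The placebo level of 0.56 does not enter the formula for a difference of two means. From Section 8.5: each dose is compared with placebo.

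**1. Reproduce the stated figure.**
- SE = SD × √(2/n) = 0.4 × √(2/30) = 0.1033.
- Half-width = 1.645 × 0.1033 = 0.1699, which rounds to 0.17. With a t quantile it is 0.173 (58 df) or 0.172 (87 df).
- Inverse: n = 2 × (1.645 × 0.4 / 0.17)² = 29.96, i.e. 30.

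**2. Try other readings of the claim.** None gives 0.17:

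| Reading | Difference |
|---|---|
| One-sided 90% bound | 0.132 |
| Two-sided 95% CI half-width | 0.202 |
| Two-sided 10% level, 80% power | 0.257 |
| Two-sided 10% level, 90% power | 0.302 |
| One-sided 10% level, 80% power | 0.219 |
| One-sided 10% level, 90% power | 0.265 |

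**3. Chance that the CI excludes zero if the true difference is 0.17.**
- Φ(0.17/0.1033 − 1.645) = Φ(0.00) = 50%. With the noncentral t it is 49.3% (58 df) or 49.5% (87 df).
- Because the SD is only approximate: 59% at SD 0.35 and 43% at SD 0.45.

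**4. True difference needed at 30 per group.**
- For 80%: (1.645 + 0.842) × 0.1033 = 0.257, which is 0.257/0.56 = 46% of the placebo level.
- For 90%: (1.645 + 1.282) × 0.1033 = 0.302, or 54%.
- For comparison, 0.17/0.56 = 30%.

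**5. Effect of baseline adjustment.** The residual SD is 0.4 × √(1 − r²), where r is the correlation between the baseline and on-treatment proportions. The protocol gives no value, so r is an assumption here:

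| Assumed r | Residual SD | CI half-width | Chance at true 0.17 | Difference for 80% |
|---|---|---|---|---|
| 0 | 0.400 | 0.170 | 50% | 0.257 |
| 0.3 | 0.382 | 0.162 | 53% | 0.245 |
| 0.5 | 0.346 | 0.147 | 60% | 0.222 |
| 0.7 | 0.286 | 0.121 | 75% | 0.183 |
| 0.8 | 0.240 | 0.102 | 86% | 0.154 |

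An 80% chance at a true 0.17 needs a residual SD of 0.17 / (2.487 × √(2/30)) = 0.265, i.e. r of about 0.75.

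**6. Withdrawals.** Fewer contributing patients would widen the interval and lower every probability above. The protocol gives no rate, so only the direction can be stated.

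**The case against.** The strongest reply is that nothing has been miscalculated. The figure follows exactly from its inputs, the sentence ties it to a 90% CI, and no power is claimed that could be contradicted. Sizing an estimation-based phase IIb trial by the precision of its interval is legitimate. All of this stands, and a reader who inferred an arithmetic error in Section 8.2 would be mistaken. It does not rescue the description: precision would be stated as a half-width, whereas the sentence speaks of ability to detect. Naming the interval does not tell the reader that the chance of detection at 0.17 is about one half.

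A second reply is that the planned analysis adjusts for a four-week baseline of the same variable, so 50% need not be the sensitivity of the actual analysis. This also stands. At an assumed correlation of 0.8 a true 0.17 would be found 86% of the time. But Section 8.2 takes no credit for adjustment and gives no correlation, so the protocol supports neither 50% nor 80% for the ANCOVA. The 50% belongs to the unadjusted calculation that Section 8.2 presents.

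Two further inferences are tempting and unsupported:
- That Section 8.5 contradicts Section 8.2. Section 8.5 presents the same 90% intervals that Section 8.2 names, and Section 8.2 claims no hypothesis test. Whether the sentence ruling out statistical comparisons sits well beside the ANCOVA is a separate question, internal to Section 8.5, and does not bear on the 0.17.
- That a programme decision rests on 0.17. The protocol contains no go/no-go rule tied to that value or to an interval excluding zero, and the reported interval will itself show whether 0.17 remains compatible with the data.

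**Conclusion.** The point holds as a fault of description. Section 8.2 presents as a detectable difference what is, on its own inputs, the expected half-width of the unadjusted 90% CI. With 30 per group and SD 0.4, the interval excludes zero with probability of about 50% at a true difference of 0.17 and about 80% at about 0.26, roughly 1.5 times larger (0.257/0.17).

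These figures assume a two-sided interval, equal SDs of 0.4, no covariate adjustment, and all 30 patients per group contributing. Baseline adjustment could raise the probability at 0.17 to 60%–86% for assumed correlations of 0.5 to 0.8; losses would lower it. The identity of 0.17 with the half-width is certain; the sensitivity of the planned ANCOVA cannot be fixed from the protocol. The matter is worth correcting, but no estimate, interval or study procedure depends on it.

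**What to change.** Keep 90 randomised patients and replace the first sentence of Section 8.2 with wording such as:

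*With 30 patients per group and an SD of 0.4, the unadjusted 90% CI for each ticagrelor–placebo difference has an expected half-width of about 0.17. The probability that this CI excludes zero is about 50% at a true difference of 0.17 and about 80% at a true difference of about 0.26.*

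Optionally, add the half-width under the baseline-adjusted model for a stated range of correlations, labelled as assumptions (for example 0.147 at 0.5 and 0.102 at 0.8).

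The cost is one or two sentences of text and a less favourable headline figure. No patients, procedures or analyses change.
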